6.2 Evaluation Schedule

The first visit is for participant screening and the second visit for confirming eligibility and documenting baseline status. Randomization will be computer-generated and CCs at each site will be notified of participants who are assigned to the intervention arm only. The CCs will then contact the intervention participants and schedule their initial and subsequent intervention visits directly with participants. Reviews by the team (diabetologist, psychiatrist, and CC) will happen weekly and the intensity of discussion on each participant will depend on CC and DS-EHR prompts and needs of the participants (well-controlled participants will require minimal discussion, while poorly-controlled participants may require more intensive discussion).

For the **intervention arm**: The CC will motivate and monitor participants' progress. The CC will update the participant's medications and labs plus PHQ-9 values in the DS-EHR and will provide a dashboard printout of participants' progress and suggested treatment plans and/or modifications for physicians to review at every case review meeting. The **usual care physician** will assess the participant and accept or modify the prompt (providing a reason if he/she chooses to modify the prompt). The case of this same participant will then be discussed, along with all other participants at the site weekly or bi-weekly case review meeting and the case review team will continue with or recommend modifications to the physician's and DS-EHR's care plan for the patient. If the case review team recommends modifications to the care plan these will be accepted or modified in a final review step by the usual care physician. The CC will update the participant and the DS-EHR system; address any barriers to care and motivate him/her to achieve risk factor management goals and confirm the next appointment dates. The CC will continue to facilitate the participant's adherence to appointments and self-management using DS-EHR reminders and phone calls.

For ALL participants: The blinded outcomes assessor at each site will independently contact all participants (intervention and control) to schedule post-randomization visits for study assessments. All other intermediate visits by the participants will be documented as they routinely are in participant's clinical case notes.

For all randomized participants, the post-randomization follow-up period will be 36 months. The study staff at each site involved in executing the study procedures includes:

- **Lead Site Investigator/Co-investigator/Sub-investigator:**
 - Site PI: Oversee all trial-related procedures (recruitment, screening, enrollment, randomization, and follow-up of participants for medical evaluation)
 - Co-investigator or coordinator to support recruitment and retention activities
- **Blinded Outcomes Assessor:**
 - **Screening and Outcomes Assessments:** a research physician or nurse that will perform screening evaluations, baseline and six-monthly history and physical examination and enters data into DS-EHR system, which randomizes participants into trial arms.
- **Care Coordinator:**
 - Motivates intervention participants to self-manage and self-monitor their conditions;
 - Monitors intervention participants and enters PHQ-9 and blood testing (glucose, HbA1c, BP, and cholesterol levels) data from clinic report forms regularly into DS-EHR and follows prompts regarding case reviews
 - Coordinates with diabetologist and psychiatrist to conduct case review meetings for intervention participants on a weekly or bi-weekly basis

- Supplies the intervention participants' management plans (generated from the DS-EHR) to study physicians at case review meetings
- Conveys any treatment plan changes to intervention participants and continues monitoring until 36 months post-randomization
- **Usual Care Physicians (diabetes or primary care physicians at each site):**
 - Routine care for participants, whether control or intervention arm
 - Attend continued education training on managing diabetes and depression
 - For intervention participants, assess output prompts from DS-EHR system and accept or reject implementation of this care plan, providing reasons for any rejection
- **Case Review Specialists (psychiatrist and diabetologist at each site):**
 - Discuss all participants' cases in the intervention arm on a weekly or bi-weekly basis
 - Recommend treatment maintenance or changes based on the outputs of the DS-EHR and clinical judgment

6.2.1 Screening (Pre-randomization)

Based on clinic records, any eligible subjects (those with poorly controlled HbA1c, BP, or lipids within the previous six months and no other obvious exclusion criteria) will be contacted for depression screening. Screening with PHQ-9 (maximum of 4 weeks before randomizing) for all potential participants will be conducted in-person or via the phone. Eligible participants from the first screening visit will be advanced to a more detailed screening visit. The second screening visit is the first time participants are required to present at the clinic.

Screening Visit 1

Potentially eligible participants will interact with a site screening officer via in-person or phone visit. The visit will include:

- Verbal consent to screen and also to notify participant's usual care provider if he/she is found to have co-morbid depression and diabetes
- Collecting contact information
- Assessing basic medical history (general Inclusion/Exclusion Criteria items)
- PHQ-9 assessment

The participants who do not meet eligibility criteria for the trial will be notified of their status. The participants who are still eligible for the study after this 1st visit will be asked to present fasting (minimum of 8 hours) for detailed screening visit (including laboratory tests and questionnaires).

Screening Visit 2 – detailed assessment (by blinded outcomes assessor)

Within 4 weeks after Screening Visit 1 (PHQ-9), the participant will be invited to present to the clinic in a fasting state for informed consent (by the site investigator or a co-investigator) and detailed screening and baseline visit (please see [Table 44](#)):

- Urine sample for urine albumin:creatinine ratio

- Blood sample for measurement of Hemoglobin A1c and blood chemistries (serum creatinine, sodium, potassium, and ALT) to determine if existing medical conditions would exclude an individual from participating in the study
- Baseline Symptoms Checklist (SCL-20) depression questionnaire
- Questionnaires to exclude other psychiatric illnesses (e.g., bipolar disorder, psychosis, reduced cognitive function)
- Fasting venous blood sample for glucose and lipids (triglycerides, total cholesterol, HDL cholesterol, and LDL [calculated])
- Blood pressure and heart rate
- Height, weight, BMI (calculated), waist circumference
- Data will be entered into DS-EHR for randomization

Those potential participants who do not meet eligibility criteria will be notified of their status at the clinic and will not undergo further testing. Those individuals still meeting the inclusion/exclusion criteria will be told that they will either be contacted by a CC if assigned to intervention arm or to continue visiting the clinic as guided by their usual care physicians.

For all participants, the outcomes assessor will:

- Complete **data entry for each participant into the DS-EHR**, which includes medical and family history, medications, and mental health evaluations.

6.2.2 Follow-up Study Visits (0, 6, 12, 18, 24, and 36 months post-randomization)

All participants (intervention and control) will be invited to present for the 6-monthly follow-up visits. All participants will have to obtain all investigations: venous FBG, HbA1c, lipid profile, serum creatinine, and other blood biochemistries if necessary, SCL-20, and any complication screenings deemed necessary (urine albumin:creatinine ratio, eye exam, and ECG) prior to the visit. All participants will be required to present the lab results at the visit, if the site does not have a system in place to obtain the laboratory results independently. Participants will be contacted by a study coordinator or the outcomes assessor and scheduled for a full assessment and blood draws.

The outcomes assessor will obtain the following data from the participants:

- Interval history, hypoglycemic events, any adverse events or serious adverse events, other complications developing or changes experienced
- Measures: Blood pressure and heart rate, height, weight, BMI (calculated), waist circumference
- Investigations: values from lab reports; reports of ECG, eye and/or foot exams
- Social/lifestyle habits and questionnaires: self-care (SDSCA), health utilities (HUI-3), diabetes treatment satisfaction (DTSQ), and frequency/costs of care
- SCL-20 and PHQ-9 depression questionnaires
- GAD-7 anxiety questionnaire
- Questionnaires to exclude other psychiatric illnesses (e.g., bipolar disorder, psychosis, reduced cognitive function)

Scheduling:

Follow-up of participants after they have stopped participation in the intervention will be conducted and will include monitoring and reporting any adverse experiences or outcomes. Potential reasons for early termination of study participation can be found in Section 9.7: [Non-Compliance](#)

Non-compliance is the failure to follow national, state, or local regulations governing human subject research, institutional policies related to human subject research, or the requirements or determinations of the IRB. This may pertain to the principal investigator, research staff, or any member or component of the human research protection program.

Examples of non-compliance:

- Performing human subject research without first obtaining ethics committee approval or an ethics committee declaration of exemption
- Deviating from or violating the provisions of an ethics committee-approved protocol
- Failing to secure ethics committee approval of a protocol due for periodic continuing review prior to its expiration date
- Permitting a protocol's ethics committee approval to lapse without stopping all research-related activities and submitting a closing progress report to the ethics committee, or in the event of an overriding safety concern or ethical issue such that it would be in the individual subject's best interest to continue study participation, not arranging with the ethics committee to continue those activities

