2.5 The INDEPENDENT Study

This study will develop and test an integrated depression and diabetes care model in four ambulatory diabetes clinics in India. Our evaluation plan will generate usable evidence regarding effectiveness, quality of life, and costs.²

The collaborative care intervention in this study will incorporate unique aspects of Indian culture gathered from focus group discussions and in-depth interviews with participants, family members, and health care providers at all clinic research sites. We will endeavor to make the intervention more participant-centered, develop locally-understandable educational materials for participants in India, and identify ways to overcome stigma of mental health disorders while facilitating trustful therapeutic relationships between nurse managers and the participants and their families.

Several additional benefits will emerge from this study, including: (a) identifying unrecognized depressive symptoms among several hundred diabetic patients and working with their regular providers to manage this appropriately; (b) training a cadre of care coordinators (CC) who can motivate better self-care for high-risk individuals; (c) offering a toolbox of therapeutic options (family-centered or other culturally-sensitive activation models such as spirituality, yoga, or meditation) in order to customize care according to the individual's preferences; and (d) developing software technology that prioritizes participants for review,

prompts treatment plan recommendations and modifications, and makes case review meetings efficient by providing an overview of key participant indicators in one place (the “dashboard”).

3 Study Design

The study is a four site, single-blind, individually randomized controlled implementation trial. Blinding outcome assessments and randomization will limit biases and evenly distribute participant characteristics.

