Data regarding health utilization, costs, and quality of care will be collected through clinic chart reviews and questionnaires. We will collect data on self-reported direct medical costs (inpatient, outpatient, prescription medication, and diagnostic services), and pharmacy use plus clinic administrative records to identify unit costs. Since out-of-pocket health expenditures predominate in India, we will also use questionnaires developed for previous studies in India.²⁴ The questionnaire will capture direct non-medical (participant time spent traveling to and attending appointments) and indirect costs (lost productivity associated with illness or premature mortality). Data regarding patient-centered outcomes such as treatment satisfaction, quality of life and utility (reflects participants' judgments regarding different health states on a continuum from 0.0 [representing death] to 1.0 [perfect health]) will be collected using the instruments described in [Table 3](#).

All data will be labeled with unique participant identifying numbers that cannot be discerned without access to the coding sheet and are meaningless to study staff and lay persons.

Table 3: Study Procedures and Measures for All Participants

Variable and Tool	Method
Demographic and Anthropometric	
Age / Sex / Marital Status / Education / Occupation / Income / Migration	Q
Height / Weight / Body Mass Index / Waist Circumference	E
Depressive symptoms	
SCL-20 depression scale; PHQ-9 (Patient Health Questionnaire)	Q
Other Psychiatric Conditions	
GAD-7 (anxiety); MoCA (cognitive function); AUDIT-10 (alcohol use); DAST-10 (substance abuse)	Q
Risk Factor Control	
Glycated Hemoglobin (HbA _{1c})	B
Blood Pressure (BP)	E
Venous Fasting Lipid panel (HDL- and LDL-cholesterol, Triglycerides)	B
Tobacco Use	Q
Incidence of Complications	
Hospitalization / ER visits / Revascularization / Surgery / Dialysis	Q
Self-efficacy	
Summary of Diabetes Self-Care Activities (SDSCA) ²⁵	Q
Quality of Life / Utility / Satisfaction	
Health Utilities Index (HUI-3)	Q
Diabetes Treatment Satisfaction Questionnaire	Q
Costs and Quality of Care	
Costs of Care (direct, indirect costs); Health Utilization; Unit Costs	Q; R
Processes of Care (e.g., annual eye exams)	Q; R

Q = Questionnaire; E = Examination; B = Blood test; R = Records.

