7.3 Participant Burden

The initial screening questionnaire will require 5 minutes of explanation and opportunity for questions and 10 minutes to complete the PHQ-9 questionnaire, while the travel time to the clinic will vary by distance to the clinic. The more detailed screening assessment to identify reasons that would make a participant ineligible will take approximately 60 minutes to complete. This baseline assessment visit requires traveling to the clinic and undergoing detailed explanation and documentation of informed consent, detailed medical history, clinical examination, anthropometric measurements, and collection of biochemical specimens. All participants enrolled in the trial (whether enrolled in the intervention arm or usual care arm) will also be requested to return to the clinic for follow-up assessments at 6, 12, 18, 24 and 36 months and unscheduled visits are recommended if the participants are not well or it is deemed necessary by the usual care physicians or the case review specialists (these “interim” visits will be shorter than the baseline visit and will be completed by the CC for intervention arm participants and the usual care physician for control participants – documentation in the DS-EHR is required for intervention arm participants, but not control arm participants). At full six-monthly visits, the outcomes assessor will administer detailed questionnaires regarding medical history, self-care activities, depressive symptoms, quality of life, satisfaction, and costs of care, in addition to clinical examination and biochemical measures collected at the clinic laboratory (Table 4). Each visit will require travel to the clinic and approximately 30 minutes to complete questionnaires and 15 minutes to complete the laboratory sample collection. The study will pay all costs associated with these 5 visits (0 (baseline) plus 6, 12, 18, 24 and 36 month time-points) for all participants (intervention arm and usual care), including consultation fee for nurses and research staff, and all measurement tools and laboratory costs. Participants will be provided with 200 rupees to cover their travel and refreshment expenses per visit.

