Participants randomized to the usual care group will have no additional direct contact with the study staff. The routine care providers of usual care participants will be provided with written guidance on how to manage depressive symptoms and provide the most updated evidence-based guidelines for care of diabetes and CVD (e.g., American Diabetes Association guidelines). As such, the usual care providers may request usual care participants to visit the clinic more frequently or may intensify treatments. We will assess these changes at outcomes assessment visits.

Participants randomized to the intervention group will have additional visits and follow-up with the CC interventionist. These “interim” visits will involve an initial visit and at least 4 visits over the course of the 12-month active intervention. There may also be more visits and more phone contact, lasting from 10 minutes for brief progress checks to more detailed 60-minute visits to use behavioral activation or motivational interviewing techniques to encourage better self-care. Participants will not be compensated for these visits and phone calls. If additional tests or changes to treatment plans are required based on guidance from the DS-EHR, the usual care physician, or our case review team, the costs for these intermediary tests or treatment adjustments will be borne by participants as this is an implementation trial. As mentioned, all study-related outcome assessment visit costs (the six-monthly “study visits”) are borne by the study team.

Throughout the screening and study process, potential participants will be treated with respect and reassured that they have the right to withdraw from the screening process or the study at any time without any consequence for their usual care. All clinic interactions and activities will be conducted in a private room and the in the preferred language(s) of the local regions to assure participants’ comfort.

8 Study Benefits

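### The only blinded role also asks participants about their care, which may reveal the arm to the person who administers the SCL-20

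*Combined protocol and SAP*

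**What the plan says.** Section 3 describes the design: "The study is a four site, single-blind, individually randomized controlled implementation trial". It relies on the blind explicitly: "Blinding outcome assessments and randomization will limit biases". Participants are not blinded. Section 6.2.1 has them told that a care coordinator will contact them if they are assigned to the intervention, and Section 5.3 gives controls no coordinator contact.

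Section 6.2.2 introduces the follow-up list with "The outcomes assessor will obtain the following data from the participants". The list includes "Interval history, hypoglycemic events, any adverse events or serious adverse events, other complications developing or changes experienced", then self-care, utilities, "diabetes treatment satisfaction (DTSQ), and frequency/costs of care", and then the SCL-20 and PHQ-9. Section 7.3 says of the six-monthly visits that "the outcomes assessor will administer detailed questionnaires regarding medical history, self-care activities, depressive symptoms, quality of life, satisfaction, and costs of care". Section 6 says the cost questionnaire covers "direct non-medical (participant time spent traveling to and attending appointments". On more frequent visits or intensified treatment in usual-care participants, Section 7.3 adds: "We will assess these changes at outcomes assessment visits".

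The stated safeguards are an independent assessor (Section 4.5), separate access rights in the electronic record (Sections 5.1 and 7.2), and improper unblinding as a reportable violation (Sections 9.6.2 and 9.6.3). Nothing fixes the order of the instruments, asks participants to keep their arm to themselves, or checks whether the blind held.

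**The concern.** The person whose ignorance of the arm protects the outcome is also the person assigned to ask about care received. An intervention participant has an initial coordinator visit, at least four more over 12 months, and telephone contact (Section 7.3). A truthful answer about appointments, costs or changes may mention them. Software access rights do not reach what is said in the room.

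A fall of at least 50% in the SCL-20 is necessary for every primary success (Section 1.1). The other components are less exposed, because HbA1c and LDL-c are laboratory values and blood pressure is taken with an automated device (Section 6). If the assessor's manner, prompting or clarification shifts SCL-20 answers in one arm, the error goes straight into the primary comparison. The natural expectation is that it would favour the intervention, but the documents do not establish the direction.

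**Working it through.** **1. When could the arm come out?** Three places set the schedule.

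| Item | Section 6.2.2 (0, 6, 12, 18, 24, 36 months) | Section 7.3 (six-monthly visits) | Table 4, months 6, 12, 18 | Table 4, months 24, 36 |
|---|---|---|---|---|
| Interval history | yes | yes (medical history) | yes | yes |
| Medications | not named in the assessor's list | not named | yes | yes |
| Treatment satisfaction | yes | yes | no | yes |
| Costs of care | yes | yes | no | yes |
| SCL-20 | yes | yes (depressive symptoms) | yes | yes |

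At 24 months, the primary time-point, all sources put satisfaction, costs and the SCL-20 at one visit. For months 6 to 18 only history and medications are free of conflict.

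**2. In what order?** The order is unclear. The bullets in Section 6.2.2 set no sequence, and the same section also counts the SCL-20 among the investigations to be completed before the participant attends.

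**3. The plan's own sample size, for scale.** Inputs from Section 4.1 are 30% vs 15%, 80% power and a continuity correction. Two-sided alpha of 0.05 is assumed because none is stated.
- Uncorrected n per arm = [1.96√(2 × 0.225 × 0.775) + 0.842√(0.30 × 0.70 + 0.15 × 0.85)]² / 0.15² ≈ 120.5.
- Corrected n = (120.5/4) × [1 + √(1 + 4/(120.5 × 0.15))]² ≈ 133.5, so 134 per arm and 268 in total.
- 268/0.80 = 335. Both stated figures reproduce, and this point does not change them.

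**4. Illustrative shift in SCL-20 response.** The 30% usual-care response is the 12-month rate from the cited trial in Section 4.1. The 0.1-point shift on the 0–4 mean-item scale (0.1 × 20 items = 2 of 80 points) and the SD of change of 0.6 to 0.8 are assumptions. Absolute change with a fixed cut-off stands in for the percentage criterion. A 30% response corresponds to z = −0.524, and the shifted response is Φ(−0.524 + 0.1/SD).
- SD 0.8: Φ(−0.399) = 34.5%, up 4.5 points.
- SD 0.7: Φ(−0.381) = 35.2%, up 5.2 points.
- SD 0.6: Φ(−0.357) = 36.0%, up 6.0 points.

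**5. Carry to the composite.** Section 4.1 puts 15% composite success beside 30% SCL-20 response in usual care, and 30% beside 60% with the intervention. Both ratios are 0.5. If half of the extra responders also meet the cardiovascular criterion, the composite moves by 4.5 × 0.5 ≈ 2.3 to 6.0 × 0.5 = 3.0 points. That is 15% to 20% of the 15-point design difference.

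**6. Effect on the false-positive rate.** Assume no true difference, 15% in both arms, 134 evaluable per arm, two-sided 0.05, no continuity correction, and a bias b added to the intervention arm. The chance of significance is Φ[(b − 1.96·se₀)/se₁] + Φ[(−b − 1.96·se₀)/se₁], where se₀ is the pooled and se₁ the unpooled standard error.
- b = 0: 5.0%.
- b = 0.02: se₀ = 0.0448 and se₁ = 0.0448, giving 0.065 + 0.008 = 7.3%.
- b = 0.03: se₀ = 0.0453 and se₁ = 0.0453, giving 0.097 + 0.004 = 10.1%.

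**The case against.** The strongest reply is that no document shows a question about coordinators. The cost questionnaire is not reproduced, and Section 10.2 takes direct medical costs mainly from charts and administrative records. Control participants may also attend more often, have treatment intensified or seek mental-health care (Sections 7.1.1 and 7.3), and usual-care physicians treat both arms. A list of visits or drugs therefore does not identify the arm by itself. This stands, and the claim is limited to what these conversations may reveal.

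Second, the SCL-20 is a fixed-response scale that the participant answers (Appendix B), so the assessor does not rate severity. This also stands and limits the likely size. It does not remove the concern, because Section 7.3 has the assessor administer the questionnaires and Section 4.4 expects some participants who cannot read.

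Third, participants' own knowledge of their arm may bias a self-reported scale at least as much, and re-ordering the visit does not touch it. This stands as a separate limitation.

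A reader might infer three stronger things. One is that the arm is certainly exposed from month 6, but satisfaction and costs at months 6 to 18 depend on which section governs. Another is that the SCL-20 follows the care questions because it is listed after them, but the list is not a sequence. The third is that the bias equals about one third of the design difference. That sets a 4.5 to 6 point shift in SCL-20 response against a 15-point difference in the composite, which are different quantities.

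**Conclusion.** The point holds as a risk to the blind, not as a demonstrated break. The only blinded role is assigned conversations that may disclose the arm, it also administers the component every primary success needs, and no stated safeguard covers what participants say. At the 24-month visit the sources agree that satisfaction, costs and the SCL-20 fall together.

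The documents give no size for the bias. Under the stated assumptions (0.1-point shift, SD 0.6 to 0.8, half of responders meeting the cardiovascular criterion) the composite moves by about 2 to 3 points, and the false-positive rate rises from 5% to about 7% to 10%. That is modest against a 15-point target. It is still worth preventing because prevention costs almost nothing.

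**What to change.** Change Sections 6.2.1, 6.2.2 and 7.3 as follows.

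1. Make the SCL-20 the first procedure at every study visit (at baseline, the first after consent), before any history, medication, satisfaction or cost question. Use the same mode throughout, with items read verbatim wherever an interviewer administers it. Baseline precedes randomisation, but it must match follow-up because the endpoint is a percentage change. Reconcile this with the Section 6.2.2 text that has the SCL-20 completed before attendance, and reconcile the satisfaction and cost schedules in Sections 6.2.2 and 7.3 with Table 4.
2. When scheduling, and again at the start of each visit, ask participants not to tell the assessor who provides their care.
3. Have the assessor record a guess of arm at 24 months, straight after the SCL-20, and report it by arm.

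The cost is a minor re-ordering of the visit and one form item, with no new visit, test or change in sample size. Order alone does not erase what an assessor learned at an earlier visit. Item 2 reduces that risk, and item 3 gives some indication of what remains.

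Wider changes, such as self-completion of the SCL-20 or moving history and adverse-event taking to a coordinator, are not recommended. Self-completion would make the mode vary with literacy and leave open who reviews the item in Appendix B that triggers the self-harm protocol. The coordinator option would move clinical history away from the research physician or nurse.
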